6.3.2 Primary Safety Endpoint

The primary safety endpoint is the rate of 12-month freedom from major adverse events. Major adverse events are defined as: clinical perforation, clinical migration, clinical fracture, embolization of the filter or filter fragments to the heart or lungs, IVC thrombotic occlusion, new symptomatic DVT while a filter is indwelling, access site complications with clinical sequelae, and procedure-/device-related death. Analysis of the primary safety endpoint will be performed separately for each filter type (i.e., each stratum).

Events occurring after filter retrieval (i.e., through the 1-month post-retrieval follow-up period) will be collected, but only the events of access site complications with clinical sequelae and procedure-related death will count against the primary safety endpoint. Other events (i.e., potentially new DVT without symptoms) will be reported as a secondary measure.

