6.3.3 Secondary Endpoints

The secondary endpoints include:

- Rate of technical placement success and 12-month freedom from new symptomatic PE while a filter is indwelling for the combined patient population
- Rate of 12-month freedom from major adverse events for the combined patient population

- Rate of 12-month freedom from Grade 2 or Grade 3 filter leg interaction with the IVC, filter migration, filter fracture, and filter embolization for both the individual stratum and the combined patient population

All primary and secondary endpoints will also be reported at 24 months. In addition, analysis of the following secondary measures will be performed separately for each filter type (i.e., each stratum) and for the combined patient population:

- Filter leg interaction with the IVC wall
- Clinical perforation
- Migration > 2 cm (including direction)
- Symptomatic PE (occurring before and after filter retrieval)
- PE (occurring before and after filter retrieval)
- IVC thrombotic occlusion (occurring before and after filter retrieval)
- Symptomatic DVT (occurring before and after filter retrieval)
- DVT (total incidence and new incidence; occurring before and after filter retrieval)
- Retroperitoneal hematoma
- Hematoma at access site
- Infection at access site
- Thrombosis at access site
- Death
- Filter tilt (with measurement)
- Filter fracture
- Filter embolization
- Filter deformation
- Length of procedure (insertion and retrieval)
- Length of ICU stay
- Length of hospital stay
- Technical placement success
- Filter retrieval attempts
- Technical retrieval success
- Failed retrieval attempts, with reason for failed attempt
- Retrieval-related complications
- Adverse events occurring after filter retrieval
- Delivery system performance

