7.5 Filter Placement Procedure

- Diagnostic imaging will be performed prior to study enrollment to verify anatomical study criteria.
- Only one Cook IVC filter should be placed in each patient. The Cook IVC filter should be implanted in accordance with the respective IFU (i.e., caudal to the renal veins).
- Completion imaging will be performed to assess filter position (including tilt) and to assess the vena cava for evidence of injury.

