8.1.1 Primary Effectiveness Hypothesis

The primary effectiveness endpoint is the rate of technical placement success and 12-month freedom from new symptomatic PE while a filter is indwelling. The analysis requires that the performance goal of 90% be met for technical placement success and freedom from new symptomatic PE at 12 months while a filter is indwelling. The

performance goal was derived based on what are considered clinically acceptable rates for technical placement success and new symptomatic PE in the overall population.⁴⁸ The performance goal will be said to have been met provided the null hypothesis is rejected in favor of the alternative with a one-tailed exact binomial test at the 0.025 level. The hypothesis will be tested only for patients receiving Celect[®] filters. Given that π is the probability that a randomly selected patient did not experience any technical placement failure or new symptomatic PE within 12 months while a filter is indwelling, the null and alternative hypotheses are as follows.

Null Hypothesis: The rate of technical placement success and 12-month freedom from new symptomatic PE while a filter is indwelling, π , does not meet the performance goal (90%).

$$H_0: \pi \leq 90\%$$

Alternative Hypothesis: The rate of technical placement success and 12-month freedom from new symptomatic PE while a filter is indwelling, π , meets the performance goal (90%).

$$H_a: \pi > 90\%$$

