APPENDIX C

Definitions

Access site complications with clinical sequelae - Arteriovenous fistula, hematoma, or bleeding requiring transfusion (≥ 2 units), hospitalization (either admission or extended stay), or further treatment.

Access site thrombus – Occlusive or nonocclusive thrombus developing at venotomy site after filter insertion or retrieval, documented by ultrasound or other imaging.

Adverse events – Definition may be found in applicable regulations.

Adverse device effects – Definition may be found in applicable regulations.

Clinical fracture – A loss of structural integrity (breakage or separation) of the filter identified by imaging and associated with clinical sequelae and/or requiring intervention.

Clinical migration – Caudal or cranial movement of a filter resulting in surgical or endovascular intervention.

Clinical perforation – Protrusion of filter legs through the wall of the IVC causing hemorrhage or hematoma or touching, impressing, or perforating another organ (e.g., liver, bowel, aorta, psoas muscle, vertebral body, lymph nodes). Acute perforation occurring during placement of the filter is considered a placement problem. Documented using CT.

Deep vein thrombosis (DVT) – Thrombus in the deep veins, usually of the lower extremities or pelvis. Documented by contrast venography, duplex ultrasound, CT, or magnetic resonance (MR) venography. The proximal extent of thrombus should be identified.

Device deficiencies – Definition may be found in applicable regulations.

Filter deformation – Insufficient opening of filter (i.e., filter legs do not adjust themselves to the size of the IVC), collapse of filter, uneven distribution of filter legs, bending of filter, or crossing or entangling of two or more filter legs.

Filter embolization – Post-placement movement of the filter or its components to a distant anatomic site completely out of the target zone (i.e., heart/lungs). Documented by imaging or autopsy.

Filter fracture – Any loss of structural integrity (breakage or separation) of the filter identified by imaging or autopsy. Documented by imaging or at autopsy.

Filter leg interaction with the IVC¹ –

- Grade 0: Normal; filter strut confined entirely within the IVC.
- Grade 1: Filter strut is immediately adjacent to the external aspect of the IVC wall (likely reflecting tenting of the IVC wall).

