- Grade 2: Filter strut is entirely outside of the IVC lumen and within the retroperitoneum as evidenced by a “halo” of retroperitoneal fat around axially viewed strut.
- Grade 3: Filter strut is touching, impressing, or perforating another organ (e.g., liver, bowel, aorta, psoas muscle, vertebral body, lymph nodes).

Filter migration – Change in filter position compared to its deployed position (cranial or caudal). Migration will be classified as significant (i.e., ≥ 20 mm) or insignificant (i.e., < 20 mm). Documented by plain radiograph, CT, or venography.

Filter tilt – Angle of the longitudinal axis of the filter with respect to the longitudinal IVC axis. Tilt will be classified as significant (i.e., $\geq 16^\circ$ relative to the IVC longitudinal axis) or insignificant (i.e., $< 16^\circ$ relative to the IVC longitudinal axis). A filter is considered free of tilt if it appears centered in the IVC. Documented by plain radiograph or venography.

¹ Oh JC, Trerotola SO, Dagli M, Shlansky-Goldberg RD, Soulen MC, Itkin M, et al. Removal of retrievable inferior vena cava filters with computed tomography findings indicating tenting or penetration of the inferior vena cava wall. *J Vasc Interv Radiol.* 2011;22:70-74.

IVC thrombotic occlusion – Presence of an occluding thrombus in the IVC occurring after filter placement. Documented by ultrasound, CT, MR, venography, or autopsy. Methods of diagnosis should be noted, along with extent of thrombus. May be symptomatic or asymptomatic.

Major adverse events – Events of clinical perforation, clinical migration, clinical fracture, embolization of the filter or filter fragments to the heart or lungs, IVC thrombotic occlusion, new symptomatic DVT while a filter is indwelling, access site complications with clinical sequelae, and procedure-/device-related death.

Premature release of filter – The filter is released from the deployment system before the physician intended.

Procedure-/device-related death – Death directly attributable to the filter or filter placement or retrieval procedure itself, documented by clinical findings, imaging, or autopsy, or as adjudicated by a Clinical Events Committee.

Pulmonary embolism (PE) – Emboli to lungs via the pulmonary artery, which can arise from deep venous thrombosis in the lower extremities or pelvis. Documented using pulmonary arteriography, cross-sectional imaging, or significant change in ventilation/perfusion lung scan, or at autopsy. PE will be categorized by type.²

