Pulmonary embolism (PE), massive – Acute PE with sustained hypotension (systolic blood pressure < 90 mmHg for at least 15 minutes or requiring inotropic support, not due to a cause other than PE, such as arrhythmia, hypovolemia, sepsis, or left ventricular [LV] dysfunction), pulselessness, or persistent profound bradycardia (heart rate < 40 bpm with signs or symptoms of shock).

² Jaff MR, McMurtry MS, Archer SL, Cushman M, Goldenberg N, Goldhaber SZ, et al. Management of massive and submassive pulmonary embolism, iliofemoral deep vein thrombosis, and chronic thromboembolic pulmonary hypertension: A scientific statement from the American Heart Association. *Circulation*. 2011;123:1788-1830.

Pulmonary embolism (PE), submassive – Acute PE without systemic hypotension (systolic blood pressure \geq 90 mmHg) but with either right ventricular (RV) dysfunction or myocardial necrosis, where:

RV dysfunction is defined as the presence of at least 1 of the following:

- RV dilation (apical 4-chamber RV diameter divided by LV diameter $>$ 0.9) or RV systolic dysfunction on echocardiography;
- RV dilation (4-chamber RV diameter divided by LV diameter $>$ 0.9) on CT;
- Elevation of BNP ($>$ 90 pg/mL);
- Elevation of N-terminal pro-BNP ($>$ 500 pg/mL); or
- Electrocardiographic changes (new complete or incomplete right bundle-branch block, anteroseptal ST elevation or depression, or anteroseptal T-wave inversion).

Myocardial necrosis is defined as either of the following:

- Elevation of troponin I ($>$ 0.4 ng/mL) or
- Elevation of troponin T ($>$ 0.1 ng/mL).

Pulmonary embolism (PE), low-risk – Acute PE and the absence of the clinical markers of adverse prognosis that define massive or submassive PE.

Serious adverse events – Definition may be found in applicable regulations.

Serious adverse device effects – Definition may be found in applicable regulations.

Significant trapped thrombus in filter – Thrombus filling $>$ 25% of the filter.

Technical placement success – Deployment of filter in a location suitable to provide sufficient mechanical protection against PE with no filter deformation, fracture, premature release, or clinical migration.

Technical retrieval success – Endovascular retrieval of complete filter.

Unanticipated serious adverse device effects – Definition may be found in applicable regulations.

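### As the definitions stand, a non-fatal acute caval perforation recognised at filter placement can count against neither primary endpoint

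*Combined protocol and SAP*

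**What the plan says.** **Safety.** Section 6.3.2 begins its list of components thus: "Major adverse events are defined as: clinical perforation, clinical migration, clinical fracture". The remaining components are embolization, IVC thrombotic occlusion, new symptomatic DVT, access site complications with clinical sequelae, and procedure- or device-related death. Appendix C defines clinical perforation as protrusion of filter legs through the caval wall with hemorrhage, hematoma or involvement of another organ, documented by CT. Within that definition stands the sentence "Acute perforation occurring during placement of the filter is considered a placement problem".

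**Effectiveness.** Section 8.1.1 counts as a success a patient who "did not experience any technical placement failure or new symptomatic PE within 12 months while a filter is indwelling". Appendix C defines technical placement success as deployment in a location that gives adequate protection, "with no filter deformation, fracture, premature release, or clinical migration".

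**Detection and reporting.** Section 7.5 requires completion imaging in part "to assess the vena cava for evidence of injury". Section 6.3.3 includes the secondary endpoint "Rate of 12-month freedom from Grade 2 or Grade 3 filter leg interaction with the IVC" (with other filter events) and, among the secondary measures, "Retroperitoneal hematoma". Section 12.1 has the Clinical Events Committee (CEC) judge whether events are related to the procedure, technique or device. Section 12.2 covers adverse event reporting.

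**The concern.** The perforation sentence hands the event to the placement side of the plan, but the placement definition does not receive it. The plan looks for caval injury at the end of every placement, yet no written rule says which primary endpoint a perforation found there counts against. It would have to be assigned once an event is known, or it would drop out of both primary results. Section 2.0 says that the study is meant to address the regulator's concerns about IVC filters, and Section 4.0 names perforation of the IVC among those concerns. The classification should therefore be fixed in advance, even if the event is rare.

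**Working it through.** **1. Trace one event.** Take an acute perforation during placement that bleeds or reaches another organ. The patient survives, the filter is intact and well positioned, and no later CT shows a leg in contact with an organ.

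| Place in the plan | Does the event count? |
|---|---|
| Clinical perforation (Appendix C) | No, on the natural reading: it is called a placement problem instead |
| Access site complications (Appendix C) | No: the bleeding and hematoma are not at the access site, and Section 6.3.3 lists retroperitoneal hematoma separately, as a secondary measure |
| Related death (Appendix C: "Death directly attributable to the filter or filter placement or retrieval procedure itself") | No: the case is non-fatal |
| Other major adverse events | No: nothing migrated, fractured, embolized or thrombosed |
| Technical placement success (Appendix C) | Still met: location suitable, and none of the four listed faults |
| New symptomatic PE | No |

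The patient is a success on both primary endpoints.

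**2. Reproduce the plan's sample sizes (Section 8.3).** Exact one-sided binomial test, alpha 0.025.
- Effectiveness, 90% against 98.4%, n = 70: at least 68 successes needed, actual alpha 0.0242, power 0.898 (stated 0.9).
- Safety, 80% against 92.2%, n = 88: at least 78 needed, actual alpha 0.0238, power 0.919.
- Attrition of 72%: 88 / 0.28 = 314.3, so 315. The planned 320 leave 320 × 0.28 = 89.6.

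**3. How common might the event be?** The documents give no rate. Section 4.0 covers 41 + 554 + 129 = 724 patients and describes no acute perforation at placement; the one vena cava injury mentioned followed a retrieval. Table 4.3 gives 0% for perforation with clinical sequelae. Exact (Clopper-Pearson) 95% upper limits for zero events, 1 − 0.025^(1/n):
- n = 724: 0.508%, or 0.00508 × 320 = 1.6 patients.
- n = 129 (Celect only): 2.82%, or 0.0282 × 320 = 9.0 patients.

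**4. Effect on the effectiveness test if the event counted there.** Assume a drop of 0.5 points, close to the 724-patient upper limit: 98.4% becomes 97.9%.

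| n | Successes needed (failures allowed) | Actual alpha | Power at 98.4% | Power at 97.9% |
|---|---|---|---|---|
| 70 | 68 (2) | 0.0242 | 0.898 | 0.818 |
| 88 | 85 (3) | 0.0196 | 0.947 | 0.885 |
| 320 | 299 (21) | 0.0206 | >0.999 | >0.999 |

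At n = 320 the expected failures are 320 × 0.016 = 5.1 without the drop and 320 × 0.021 = 6.7 with it, against 21 allowed.

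**5. Extreme bound.** At the Celect-only upper limit the rate would be 98.4 − 2.82 = 95.58%, with power 0.451 at n = 88 and 0.971 at n = 320.

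**The case against.** The text is open to softer readings. Appendix C does not literally say that acute perforation is excluded from clinical perforation, and *placement problem* may have been meant as technical placement failure. Both are possible, but neither is written. Under the first, the sentence has no evident purpose. Under the second, the definition of technical placement success contradicts it.

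A reader might infer that such an event can never count. The documents do not support that. A fatal case counts in safety. So does one that leads to another major adverse event, and an unsuitable location, deformation, premature release or clinical migration defeats placement success. Grade 3 leg interaction uses the same organ-contact criterion as clinical perforation, so contact that persists on a symptom-driven or scheduled CT (Section 7.7) could still be classed as a major adverse event.

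A reader might also infer that the CEC has no power to assign the event. Section 12.1 describes relatedness review only, but it does not rule out endpoint assignment, and no charter is among the documents. What stands is that no written rule guides the assignment.

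Finally, one could argue for the safety endpoint: Section 8.1.2 and Table 4.2 cite the same source, and that table's 80% composite includes perforation and major procedure-related complications. That is a legitimate alternative. Assignment to placement follows the plan's own label and leaves the safety criteria alone.

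**Conclusion.** The gap is real but narrow. It covers a non-fatal acute perforation with hemorrhage, hematoma or organ involvement that is recognised at placement, with the filter otherwise well positioned and no qualifying organ contact on a later CT. On the natural reading such a patient is a success on both primary endpoints. The event can still surface as retroperitoneal hematoma, leg interaction or an adverse event, but these reports do not by themselves make it count in a primary result.

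The expected effect on either test is negligible at 320 patients. It is modest at the plan's minimum of 88 (0.947 to 0.885) and larger at the 70 given for effectiveness alone (0.898 to 0.818). These figures assume a 0.5-point rate that the documents do not give. Section 4.0 summarises significant findings, so zero means none described. A reader might take the power of 0.451 as a sign that the trial is at risk. It is not: it combines an upper limit from no events in 129 patients with the smallest analysable sample, and is a bound rather than an expectation. The case rests on having the primary endpoints fully classified before events occur.

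**What to change.** Change two definitions in Appendix C.

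1. *Technical placement success*: after clinical migration, add to the list of disqualifying events: *or acute perforation of the IVC, recognised during the placement procedure or on completion imaging, that causes hemorrhage or hematoma or involves another organ*.
2. *Clinical perforation*: let the sentence on acute perforation say that such an event, *recognised during the procedure or on completion imaging, is counted as a technical placement failure* (with the same criteria as in item 1), and that *a perforation first recognised later counts as a clinical perforation only if it meets the definition above, including CT documentation*.

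The second clause of item 2 must keep the hemorrhage, hematoma or organ-contact requirement. Without it, a symptom-free Grade 2 finding on the 12-month CT would become a major adverse event. A related death would still count in the safety endpoint as well, so a fatal case can count in both.

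The major adverse event criteria and both performance goals stay as they are. No imaging or visit is added, because Section 7.5 already requires completion imaging and the rule covers only what is recognised there. The cost is a slightly less favourable placement success rate. The 98.4% planning rate should be checked against the revised definition: it agrees with 127/129 = 98.45%, that is, the two Celect PEs in Section 4.0 and no placement failure.
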